# 2.1 PROTOCOL SYNOPSIS

The protocol synopsis and the schedule of assessments of the substudy are included in the current version of the protocol.

# 2.2 OUTCOME MEASURES

## 2.2.1 Primary Outcome Measure

The primary endpoint in this substudy is the proportion of patients with IRRs occurring during or within 24 hours after the 1st randomized infusion of ocrelizumab.

# 2.2.2 Secondary Outcome Measures

The following secondary IRR-related variables will be summarized:

- Proportion of patients with IRR overall and by dose at randomization
- Intensity of IRRs
- Proportion of patients with serious IRRs
- Symptoms of IRRs
- IRRs leading to treatment discontinuation
- Subgroup analyses according to IRR history (for example, patients with/without IRR at any previous dose)

# 2.2.3 Exploratory Outcome Measures

The following exploratory variables will be summarized:

- Proportion of patients with Common Terminology Criteria for Adverse Events (CTCAE) Grade 3 or 4 (severe or life-threatening) IRRs
- Number of CTCAE Grade 3 or 4 (severe or life-threatening) IRRs

## 2.2.4 Pharmacokinetic Analysis: Objectives and Outcome Measures

The pharmacokinetic (PK) analysis will assess any potential relationship between the primary endpoint (described above) and the maximum concentration of ocrelizumab  $(C_{max})$ .

## 2.2.5 Pharmacodynamic Outcome Measures

There are no pharmacodynamic endpoints in this study.

## 2.2.6 Safety Outcome Measures

In addition to the assessment of safety via IRRs, safety will also be regularly assessed via reporting of AEs, vital signs and laboratory data (including CD19, CD4 and CD8).

# 2.3 DETERMINATION OF SAMPLE SIZE

Determination of sample size was described as follows in the protocol (Version 7.0):

Regarding patients already enrolled into the main study, we assume that approximately 40 and 110 will receive the first dose of randomized treatment at Dose 3 or at Dose 4 / subsequent dose, respectively. In addition, since no previously enrolled patients will receive shorter infusion at Dose 2, the Sponsor plans to include approximately 550 new patients, of which approximately 500 are expected to receive the randomized treatment at Dose 2 and be evaluable for the analysis. In total, approximately 650 patients are expected to be randomized into two groups and be evaluable for the final clinical study report (CSR).

The different IRR rates at Dose 2, 3 or 4 or at subsequent dose are considered in the calculation of the pooled IRR rate. In the Opera studies (WA21092 and WA21093), 13.7%, 9.6% and 7.8% of patients had at least one IRR at Dose 2, 3 and 4, respectively, which leads to an expected pooled IRR rate of approximately 12.4% excluding Dose 1 for this substudy. Therefore, we assume an observed IRR rate in the conventional infusion group of 12.4% excluding Dose 1. The 95% confidence intervals (CIs) of the IRR rate difference between shorter and conventional infusion groups as a function of the observed IRR rate in the shorter infusion group are listed in Table 2 (below). The CIs were calculated based on the assumption of Binomial distributed IRR rates, which provide sufficient precision around the IRR rates for this substudy.

	•		,
IRR rate in conventional infusion (%)	IRR rate in shorter infusion (%)	Difference in IRR rate (%)	95% CI
12.4	12.4	0	(-5.1, 5.1)
12.4	13.4	1	(-4.2, 6.2)
12.4	14.4	2	(-3.2, 7.2)
12.4	15.4	3	(-2.3, 8.3)
12.4	16.4	4	(-1.4, 9.4)
12.4	17.4	5	(-0.5, 10.5)
12.4	18.4	6	(0.5, 11.5)

Table 295% CI of IRR rate difference under different scenarios, based on
N=650 (shown as Table 4 in Protocol Version 7.0)

CI=confidence interval; IRR=infusion-related reaction

The motivation for undertaking this IA based on approximately 400 patients has been described above in the "Background" section. To demonstrate the impact of fewer patients on the sample size calculation shown in the study protocol (Version 7.0), Table 2 above is repeated below as Table 3, the only difference being that Table 3 is now based on 400 patients rather than 650:

# Table 3 95% CI of IRR rate difference under different scenarios, based on N=400

IRR rate in conventional infusion (%)	IRR rate in shorter infusion (%)	Difference in IRR rate (%)	95% CI
12.4	12.4	0	(-6.5, 6.5)
12.4	13.4	1	(-5.6, 7.6)
12.4	14.4	2	(-4.7, 8.7)
12.4	15.4	3	(-3.8, 9.8)
12.4	16.4	4	(-2.9, 10.9)
12.4	17.4	5	(-2.0, 12.0)
12.4	18.4	6	(-1.1, 13.1)

CI=confidence interval; IRR=infusion-related reaction

Comparison of the two tables above shows that using 400 rather than 650 patients increases the expected width of the 95% CI for the between-group difference from around 10 to 11 percentage points to around 13 to 14 percentage points. Depending on the IA results, a sample size of 400 patients could be sufficient to demonstrate the acceptability of the shorter infusion.

#### 2.4 ANALYSIS TIMING

Full details of analysis timing are provided in Section 1, "Background" above.

In summary, the analysis of the substudy will be conducted after the last enrolled patient completes the 24-hour evaluation period after the 1st randomized infusion. An IA will be undertaken by the iDCC with a CCOD of 27th September 2019, including approximately 400 patients. The iDMC and Substudy DRB only will review a subset of key unblinded data summaries from this IA and the Substudy DRB will determine a) whether or not the substudy team should be unblinded, the full IA should be undertaken (all summaries, not just a subset) and this IA should be filed with health authorities or b) to place all further unblinding and preparation of data summaries on hold until all patients randomized into the substudy (approximately 650 to 700) have completed the 24-hour evaluation period after the 1st Randomized Dose, in which case this would represent the final analysis of the substudy.

## 3. STUDY CONDUCT

## 3.1 RANDOMIZATION AND BLINDING

Patients were randomized into two groups (Conventional Infusion or Shorter Infusion) in a 1:1 ratio. An independent IxRS provider conducted randomization (with use of blocked randomization) and holds the treatment assignment code. Patients were stratified by region (US / Canada / Australia vs. ROW) and the Dose at which the patient is randomized. For patients previously enrolled into the main study, randomization takes place at the next scheduled infusion visit i.e. at Dose 3, 4 or 5. For newly enrolled patients, randomization takes place at Dose 2.

Blinding of the infusion rates and the actual duration of the infusion is achieved by the following measures:

- The substudy group assignment (randomization) codes are only visible to the pharmacy personnel preparing the drug infusions and to the unblinded personnel operating the infusion pump (from now on, referred to as "infusion nurse")
- Infusions are pre-loaded and placed into standardized infusion cover bags and placed on an infusion rack, and the actual infusion administration pump is covered and operated by the infusion nurse
- The actual infusion rates and associated activities related to infusion administration are blinded to the site study team (including the study coordinator and the treating investigator), patient and the Sponsor
- The conventional-length infusion is administered as described in the main study protocol. The shorter infusion is administered within 2 hours (500 mL infusion volume at the rates as presented in Table 3 in the substudy protocol), followed immediately by administration of a separate 100mL normal saline (0.9 % NaCl) bag without any additional component over the remaining 1.5h with an approximate infusion rate of 60mL/hr. For patients randomized to the conventional-length infusion, the infusion nurse mimics a switch infusion at approximately 2 hours (timing to be adapted depending on the infusion rate adaptation during the first 2 hours). The infusion nurse checks and adjusts the infusion rates periodically as needed,

both for maintaining the correct rates of the infusion and for maintaining the blinding/masking of the two infusion groups (see Figure 1 and Figure 2 below). Adjustments needed for managing IRRs are allowed at any time and should follow the guidance from the main study protocol. Please refer to substudy protocol Section 4.3.2 Dosage, Administration and Compliance for further details on the infusion preparation and administration.

- The infusion nurse (unblinded) or the clinical nurse (blinded) collect vital signs at the time of pre-medication onwards (see Section 4.5.4 of the main study protocol). Vital signs will be reported in the electronic case report form (eCRF). The blinded treating investigator evaluates and confirms all IRRs occurring during or within 24 hours post-infusion.
- The unblinded information related to the infusion is entered into the IxRS system by the unblinded site staff member. The unblinded site staff members must keep confidential any data related to the infusion (group allocation, infusion duration and content, etc.):
  - they must not further communicate these data, neither verbally nor in writing– they must maintain the corresponding files in a locked, access-restricted location
- Additional operational measures are undertaken at local level to ensure the appropriate level of blinding of the personnel involved and the data collected
- The IxRS service provider and iDMC members have access to treatment assignment in order to fulfil their roles during the substudy

## Figure 2 Figure Blinding Procedure

[figure not shown]

#### Involvement of clinical nurse (BLINDED): All clinical assessments and follow-up

AH=antihistamine; H=hour; IVMP=intravenous methylprednisolone; OCR=ocrelizumab; PK=pharmacokinetic

# 3.2 INDEPENDENT REVIEW FACILITY

In this substudy, there is no Independent Review Facility or Reading Center to review data for the purpose of making any diagnosis or providing any outcome measure.

## 3.3 DATA MONITORING

In the interests of patient safety, an iDMC is reviewing cumulative unblinded safety data from the substudy at approximately 3-month intervals, as described in the iDMC Charter. The iDMC will discontinue its activities once the analysis is completed.

## 4. STATISTICAL METHODS

## 4.1 ANALYSIS POPULATIONS

The primary summaries of IRRs will be performed using the Intent-to-Treat (ITT) Population. The Per-Protocol (PP) Population will be used in order to evaluate the influence of major protocol deviations and as a sensitivity check of the primary analyses of IRRs. Other than analyses of IRRs, safety analyses will be based on the Safety Population only. The Safety Population will also be used as a sensitivity check of the primary summaries of IRRs. The Pharmacokinetic (PK) Population will be used for supportive analyses.

## All Patients Population

All patients enrolled into the substudy (i.e. written informed consent has been provided) will be included in the All Patients Population, whether or not they were randomized.

## ITT Population

All randomized patients will be included in the ITT Population. Patients will be analyzed according to their randomized treatment, regardless of treatment actually received.

## **PP Population**

Patients in the ITT Population with the following major protocol deviations (identified by category and sub-category) will be excluded from the PP Population. Consideration will be given to whether or not the deviation will impact assessment of the primary endpoint (i.e. IRRs):

## Category: Main Study Entry Criteria

It is not possible to provide an exhaustive list of sub-categories here. Some examples of this kind of deviation are:

- Informed consent not provided by patient for latest version of protocol ("Protocol Amendment" eCRF page)
- Patient's age at the main study screening visit was not in the range 18-55 years

#### Category: Substudy Inclusion Criteria

Sub-categories:

- Informed consent not provided by patient ("Informed consent of Ensemble Plus" eCRF page)
- Patient unable to comply with the substudy protocol, in the investigator's judgment

#### Category: Substudy Exclusion Criterion

Sub-category:

• Patient has previously experienced a serious IRR with ocrelizumab treatment

#### Category: Medication-Related

It is not possible to provide an exhaustive list of sub-categories here. Examples of this kind of deviation include failure to administer methylprednisolone and/or antihistaminic drugs in line with protocol requirements, since this may increase the chance of IRRs in those patients.

#### Category: Procedural: Infusion-Related

It is not possible to provide an exhaustive list of sub-categories here. Some examples of this kind of deviation are:

- Patients who received any randomized treatment other than that to which they were randomized (excluded from the PP Population from the time of this deviation onwards)
- Blinded site staff becoming unintentionally unblinded to a patient's blinded randomized treatment assignment
- Patients who were mis-stratified for randomization. Since the randomization is stratified by region and 1st Randomized Dose, an example of this would be a patient who started randomized treatment at Dose 2, but was incorrectly randomized from the Dose 3 randomization list in the IxRS system (and in this situation, it is impossible to know whether the patient would have received the same treatment if the stratification had been performed correctly).

#### Category: Procedural: Other

It is not possible to provide an exhaustive list of sub-categories here. An example of this kind of deviation is non-adherence to schedule of assessments.

#### Category: Other

It is not possible to provide an exhaustive list of sub-categories here. This will include any major protocol deviations detected during the study conduct not classified in one of the above categories/sub-categories.

The data sources of major protocol deviations in the clinical trial database will be Roche's Protocol Deviation Management System (PDMS), plus filenotes created to

document randomization/stratification issues encountered with the IxRS system. Entries in the PDMS system are made and maintained by study medical monitors, and will be provided in the form of an Excel file to substudy statistical programmers for incorporation into the substudy datasets. Similarly, an Excel file will be prepared to summarize all filenotes relating to IxRS technical issues, and again provided to substudy statistical programmers for incorporation into the substudy datasets.

The following programmatic data checks will be undertaken:

- Check that all patients met all main study entry criteria, based on the question "Did subject meet all eligibility criteria?" on the "Subject Eligibility" eCRF page
- Check that the patient's age at the main study screening visit was in the range 18-55 years
- Check that no patient with a serious IRR on ocrelizumab treatment prior to randomization was then randomized
- Check that each patient provided informed consent for the substudy (based on the "Informed Consent of Ensemble Plus" eCRF page)
- Check that each patient actually received the correct randomized treatment (the actual treatment is collected in the IxRS system)

## Safety Population

The Safety Population will include all randomized patients who received any dose or part of a dose of ocrelizumab treatment. Patients who received any randomized treatment other than that to which they were randomized will be analyzed according to the treatment actually received. Any patient receiving at least one shorter infusion (whether or not this is their randomized treatment) at any time during the substudy will be assigned to the shorter infusion group at all randomized doses, regardless of the randomized dose at which the patient actually first received the shorter infusion.

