It is anticipated that the patient will need to stay at the hospital or clinic for a full day for the infusion visits. Ocrelizumab infusions should be initiated and supervised by an experienced professional with access to appropriate medical support to manage severe reactions such as serious IRRs. Each ocrelizumab infusion should be given as a slow IV infusion over approximately 150 minutes (2.5 hours) for the 300 mg dose, approximately 215 minutes (approximately 3.5 hours) for the 600 mg dose for patients randomized to the conventional infusion and approximately 120 minutes (2.0 hours) for the 600 mg dose for patients randomized to the shorter infusion. The exact ocrelizumab administration rate for each group is blinded in this study.

To reduce potential IRRs, all patients will receive prophylactic treatment with 100 mg of methylprednisolone, or equivalent, administered by slow IV infusion, to be completed approximately 30 minutes before the start of each ocrelizumab infusion and an antihistaminic drug (e.g., diphenhydramine) approximately 60 minutes before each infusion of ocrelizumab. Additional premedication is recommended (see Section 4.3.3 of the main study protocol).

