6. STATISTICAL CONSIDERATIONS AND ANALYSIS PLAN

The primary analyses will be performed using the intent-to-treat (ITT) population. The per-protocol (PP) population and safety population will be used for supportive analyses. The analyses will be performed when all patients have completed the 24-hour observation period after the first randomized infusion. All the analysis will be performed for descriptive purposes and no formal hypothesis testing will be performed. Detailed specifications will be included in the SAP.

ITT Population

All randomized patients will be included in the ITT population. Patients will be analyzed according to their randomized treatment.

PP Population

The PP population will include all ITT patients without protocol deviations deemed to affect the assessment of the primary endpoint. The list of criteria leading to exclusion from the PP population will be finalized prior to database closure and documented in the SAP. Patients who receive the opposite infusion type from the randomized one will be excluded from the per protocol population.

Safety Population

The safety population will include all randomized patients who received any dose or part of a dose of ocrelizumab. Randomized patients who receive the opposite infusion type from the randomized one will be summarized in the group according to the treatment actually received.

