## 4.5 SAFETY ANALYSES

This is a descriptive study and no formal inferential statistical analyses will be performed.

Summaries of the primary endpoint (proportion of patients with IRRs occurring during or within 24 hours after the 1st randomized infusion of ocrelizumab, as described below in Section 4.5.2.1) will provide point estimates of the between-treatment difference and associated symmetric two-sided 95% CIs. These summaries will be presented both unstratified and stratified for the stratification factors of 1st Randomized Dose and region (US / Canada / Australia vs. ROW).

Safety data include but are not restricted to AE data, laboratory data, previous and concomitant treatment data, infusion information including IRR data, withdrawal data, fatalities, vital signs and dosing information.

All summaries of IRRs will be based on the ITT Population (with the exception of additional sensitivity analyses for the primary endpoint only, based on PP and Safety Populations). All other safety summaries will be based on the Safety Population.

The term "Pre-Randomization" will be used refer to the period of time before the patient is randomized into the substudy. The term "Randomized Period" will be used to refer to the period of time during which a patient receives randomized treatment in the substudy. If a randomized patient discontinues from randomized treatment, they effectively discontinue from the substudy, and after this they will either:

- a) continue to receive ocrelizumab in the main study according to conventional infusion guidelines this period of time will be referred to as "Post Substudy, On Treatment"
- b) discontinue ocrelizumab treatment entirely and enter a safety follow-up period, as described in the main study protocol – this period of time will be referred to as "Post Substudy, Off Treatment"

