## 4.5.1 Exposure to Study Medication

Within the substudy, in both randomized groups ocrelizumab is given as single infusions of 600mg at 24-week intervals. The only difference between the randomized groups is the duration of the infusion.

Patients will be considered to have received a dose of treatment if at least part of that infusion was given. If a dose is completely missed instead of delayed, the next dose number will be based on the number of previous doses received.

For each patient, the length of exposure to randomized treatment is from the date on which the patient first received randomized treatment (Substudy Day 1) until the last known alive date or CCOD, whichever is earlier. For patients who withdrew early from randomized treatment, the exposure is until the last known alive date (i.e., duration of exposure is equivalent to duration of observation period, and these terms are used interchangeably in this SAP). To summarize, the duration of exposure for a patient will be calculated as:

(Date of last contact\* – date of 1st Randomized Dose) + 1

\* Earlier of 1) date of CCOD 2) last known alive date

The following aspects of exposure to ocrelizumab will be summarized by randomized group:

- Treatment duration (weeks): frequency counts (number of patients and percentage) for 0-23 weeks, 24-47 weeks and 48-71 weeks will be presented
- Number of doses received: frequency counts (number of patients and percentage) and summary statistics (mean, SD and median) will be presented
- Total cumulative dose (derived to mg): summary statistics (mean, SD, median, lower and upper quartiles, minimum and maximum) will be presented

- Ocrelizumab infusion duration (minutes): summary statistics (mean, SD, median, lower and upper quartiles, minimum and maximum) will be presented by Randomized Dose and overall (all randomized doses).
- The number and percentage of infused patients with < 80% and ≥ 80% of the planned infusion volume will be presented, along with the number and percentage of infused patients who were pre-treated with methylprednisolone (or equivalent) only, with antihistamine only and with both methylprednisolone (or equivalent) and antihistamine. These summaries will be presented by Randomized Dose and then by Dose within Randomized Dose (and overall within Randomized Dose i.e. across all Doses).

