## 4.5.2 Adverse Events

## 4.5.2.1 Infusion-Related Reactions

IRRs are collected on the "Adverse event/IRR/MS relapse" and "Infusion Related Reaction" eCRF pages. The symptom(s) of an IRR and the IRR itself may be of different intensities. IRR symptoms (collected on the "Infusion Related Reaction" eCRF page) will be coded in MedDRA and summarized by SOC and PT. IRRs (in fact all AEs) are categorized on the "Adverse Event/IRR/MS Relapse" eCRF page as occurring 1) during infusion or 2) within 24 hours after end of infusion.

Summaries of pre-randomization IRRs and serious IRRs are described above in Section 4.3.3. In all other summaries of IRRs, only IRRs occurring during the substudy will be included. IRRs occurring after withdrawal from the substudy will not be included in these IRR summaries (but will be included in AE summaries, which will include all AEs with an onset date after the date of randomization, even if the onset is after the patient discontinues randomized treatment).

The primary endpoint of this substudy is the proportion of patients with IRRs occurring during or within 24 hours after the 1st randomized infusion of ocrelizumab. A stratified method will be applied, to take account of the two stratification factors, region and 1st Randomized Dose. The weighted average of the proportion difference across strata based on Cochran-Mantel-Haenszel weights is estimated. This approach will result in a stratified estimated difference between the proportions in the two randomized groups, which will be presented along with an associated 95% CI. This method is described by (Zhao et al. 2001) and its practical implementation is further described by (Zhang 2016). The (unstratified) estimated difference between the proportions in the two randomized by (Zhang 2016).

groups will also be presented along with an associated 95% CI. This summary will be presented for all patients, for patients with at least one pre-randomization IRR and for patients with no pre-randomization IRRs. The primary endpoint will be summarized for the ITT Population, and also for the PP and Safety Populations additionally, as sensitivity analyses. The primary endpoint will be further described in graphical barchart format (ITT Population only).

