## 4.5.2.3 Common Adverse Events

AEs will be defined as all AEs including IRRs and serious MS relapses, but excluding non-serious MS relapses. Therefore, those AEs recorded on the "Adverse event/IRR/MS relapse" eCRF page will be included.

AEs reported from randomization onwards at all randomized doses will be included in summary tables. These summary tables will show all AEs combined, and will not show any separate summaries by Randomized Dose nor Dose.

All AEs with an onset date after the date of randomization will be included, even if the onset is after the patient discontinues randomized treatment. AEs will be flagged by substudy period based on time of onset, as described at the end of Section 2 (periods are "Randomized Period", "Post Substudy, On Treatment" and "Post Substudy, Off Treatment"). For each AE recorded, the term entered by the investigator describing the event (the "reported term") will be assigned a standardized term (the "preferred term" (PT)) based on the Medical Dictionary for Regulatory Activities (MedDRA) World Health Organization (WHO) dictionary of terms. All analyses of AE data will be performed using the PTs unless otherwise specified. All AEs will be mapped to PTs and system organ classes (SOCs).

Summaries of AEs will be generated summarizing the incidence of treatment-emergent AEs only. These are defined as either: a) AEs with an observed or imputed date of AE onset which is on or after the date of 1st Randomized Dose or b) AEs with an observed or imputed date of AE onset which is before the date of 1st Randomized Dose and which worsens in intensity. An AE with a completely missing non-imputed start date will be assumed to be treatment emergent unless the AE event has a complete non-imputed end date which is prior to the date of the 1st Randomized Dose. In this substudy, the term "treatment-emergent" will always be used to mean "randomization-emergent" (it does not refer to the first dose of ocrelizumab treatment in the main study).

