# 4.5.4 Vital Signs

Vital signs parameters are systolic blood pressure, diastolic blood pressure and pulse rate (body temperature is not included -- measurement of body temperature after the main study screening visit was required in earlier versions of the protocol, but in later versions this was only required at screening, but at any time sites could record body temperature for specific reasons e.g. temperature increase).

Vital signs parameters prior to start of each ocrelizumab infusion (baseline) and at 15, 30, 45 minutes, 1, 1.5, 2, 2.5, 3, 3.5, 4, 4.5 and 5 hours post start of ocrelizumab infusion and 1 hour post end of ocrelizumab/saline infusion will be summarized (mean, SD, median, minimum and maximum). The change from baseline will also be summarized (mean, SD, median, minimum and maximum). Additionally, box plots of each vital signs parameter during the time of the infusion will be presented (by Randomized Dose).

Vital signs abnormalities are defined as follows:

- Systolic blood pressure <90mmHg or >140mmHg
- Diastolic blood pressure <50mmHg or >90mmHg
- Pulse rate <60pm or >100bpm

The number and percentage of patients with any vital signs abnormalities and with each abnormality described above will be presented, for all patients, for patients experiencing IRRs during/post-infusion and for patients not experiencing IRRs. These summaries will be presented by Randomized Dose and then by Dose within Randomized Dose (and overall within Randomized Dose i.e., across all Doses).

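### In Safety Population outputs tied to a single dose, the SAP's ever-shorter rule can label a conventional infusion as shorter; no crossover is documented and the expected effect is negligible

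*SAP*

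**What the plan says.** SAP 4.1 (Safety Population) first states an as-treated principle for patients who received an infusion other than the randomized one. It then adds that a patient with even one shorter infusion during the substudy is "assigned to the shorter infusion group at all randomized doses, regardless of the randomized dose at which the patient actually first received" it. Protocol Appendix 10, Section 6, says only that patients given the opposite infusion type "will be summarized in the group according to the treatment actually received". It does not mention patients who received both types, and it leaves detail to the SAP.

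The outputs that use this population are of two kinds.

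- **Tied to one dose.** The primary endpoint is the proportion of patients with an IRR at the 1st randomized infusion (SAP 2.2.1). SAP 4.5.2.1 says: "The primary endpoint will be summarized for the ITT Population, and also for the PP and Safety Populations additionally, as sensitivity analyses". Apart from the IRR summaries, which use ITT, SAP 4.5 says: "All other safety summaries will be based on the Safety Population". That includes vital signs, where "box plots of each vital signs parameter during the time of the infusion will be presented (by Randomized Dose"), with abnormality tables split the same way (SAP 4.5.4). SAP 4.5.1 adds: "Ocrelizumab infusion duration (minutes): summary statistics (mean, SD, median, lower and upper quartiles, minimum and maximum) will be presented by Randomized Dose".
- **Pooled over doses.** For the AE tables, SAP 4.5.2.3 says: "These summary tables will show all AEs combined, and will not show any separate summaries by Randomized Dose nor Dose".

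**The concern.** An ever-exposed label suits a cumulative table: once a patient has had a shorter infusion, later events may reasonably be counted against it. It does not suit an outcome that belongs to one infusion. A reaction at the 1st randomized infusion cannot depend on how a later infusion was given, yet under this rule the group label can.

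The relabelling runs one way: conventional infusions enter the shorter group, never the reverse. With average-risk patients this dilutes a real difference, which is not a cautious choice when the question is whether the shorter infusion is worse. What would be lost is a correctly reclassified as-treated check of the first-dose result. By-dose vital signs would also mix patients on ocrelizumab with patients on saline.

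**Working it through.** **1. The plan's own figure.** SAP Table 2 (2.3) gives -5.1 to 5.1 points for 12.4% in both groups and N=650. With 325 per group, 1.96 × sqrt(2 × 0.124 × 0.876 / 325) = 5.07 points, which agrees. For 12.4% against 18.4%, 1.96 × sqrt((0.124 × 0.876 + 0.184 × 0.816) / 325) = 5.53, giving 0.47 to 11.53 against the printed 0.5 to 11.5.

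**2. Which sequences matter.**

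| Received at 1st randomized dose | Received later | First-dose label | Later-dose label |
|---|---|---|---|
| Conventional | Shorter | Shorter (wrong) | Correct |
| Shorter | Conventional | Correct | Shorter (wrong) |

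Only the first row touches the first-dose sensitivity analysis. It can arise in two ways: (A) randomized to conventional, with a shorter infusion later by error; (B) randomized to shorter, given conventional by error at the 1st dose, with shorter later.

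**3. Base values.** Protocol 1.2 (Clinical Safety) reports 291 conventional and 289 shorter patients, with 67 and 71 having IRRs after the first randomized infusion. The difference is 100 × (71/289 - 67/291) = 1.543 points. The half-width is 196 × sqrt(0.2457 × 0.7543/289 + 0.2302 × 0.7698/291) = 6.93. The printed 23.1% fits 67/290, which would give 1.46. These are unstratified; the SAP also plans a stratified estimate.

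**4. Expected shift.** The number of crossovers, k, is not in the documents; 1, 3 and 10 are illustrations. Give each the conventional rate, p = 67/291 = 0.2302, and let j = k × p.

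- Case A, value under the rule: (71 + j)/(289 + k) - (67 - j)/(291 - k). Compare with 1.543.
- Case B, true as-treated value: (71 - j)/(289 - k) - (67 + j)/(291 + k). The rule gives 1.543.

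| k | A: rule | A: shift | B: true | B: rule minus true |
|---|---|---|---|---|
| 1 | 1.538 | -0.005 | 1.549 | -0.005 |
| 3 | 1.528 | -0.016 | 1.560 | -0.016 |
| 10 | 1.492 | -0.052 | 1.599 | -0.055 |

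In the largest planning scenario (a 6-point difference, 325 per group), k = 3 gives -6 × 3/328 = -0.055 points against a half-width of 5.5. At equal rates the expected shift is zero.

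**5. If crossover were related to IRRs.** Bounds for case A with k = 3: if all three had an IRR, 100 × (74/292 - 64/288) = 3.12, a shift of +1.58; if none did, 100 × (71/292 - 67/288) = 1.05, a shift of -0.49. These are limits, not predictions.

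**6. Vital signs.** Appendix 10, 4.3.2, runs the conventional infusion to about 215 minutes; the shorter one moves to saline at about 120. At the 2.5, 3 and 3.5 hour readings (150, 180 and 210 minutes) a mislabelled conventional patient would still be on ocrelizumab while correctly labelled patients, if infused to schedule, were on saline.

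**7. Infusion duration, if the label applies there.** The protocol plans "approximately 120 minutes (2.0 hours) for the 600 mg dose for patients randomized to the shorter infusion", against about 215 for conventional. The shorter group's first-dose mean would rise by 95k/(289 + k): 0.33 minutes for k = 1 and 0.98 for k = 3.

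**8. Opportunity at the interim.** A wrong label needs a second randomized dose. The first newly enrolled patient was randomized on 22 March 2019 (SAP 2), 189 days or 27.0 weeks before the 27 September 2019 cutoff. With 24-week dosing, few could have had two. The first already-enrolled patient was randomized 47.1 weeks before it.

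**The case against.** The strongest reply is that the rule is explicit and deliberate: the SAP supplies detail that the protocol delegates to it, and one label per patient is a recognised convention. The part about the protocol stands. A reader might infer that the SAP contradicts Appendix 10, Section 6, but that section is silent on patients who received both types. The tension lies within the SAP's own Safety Population paragraph, between the as-treated principle and its extension to every dose. Being deliberate does not give the rule a rationale for a first-dose outcome.

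Three further points also stand in whole or part.

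- **Other analyses cover much of this.** ITT follows randomization. The per-protocol rule excludes a patient only from the wrong infusion onwards, so a case A patient keeps the correct first-dose label there and a case B patient is removed.
- **The infusion-duration effect is an inference.** SAP 4.5.1 refers to the randomized group. The Safety Population AE sections use similar wording, so the as-treated label may be meant, but the text does not settle it. IRRs led to slowing or interruption in 25 shorter-infusion patients (8.7%) at the first randomized dose (Protocol 1.2). Such infusions can already lengthen that group's upper tail and blur the later vital sign readings.
- **Opportunity is narrow.** The rule covers infusions during the substudy, so elective switching under the main protocol after the substudy ended does not count.

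**Conclusion.** The point holds as a minor one. The rule mislabels a conventional infusion in dose-specific Safety Population outputs whenever a patient received both types. It reaches the first-dose IRR check only when conventional came first and shorter later.

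A reader might infer that any crossover distorts the first-dose result, or that the substudy's main conclusion is at risk. The documents support neither: shorter-then-conventional patients are correctly labelled at the first dose, and the ITT primary analysis, the remaining IRR summaries and the per-protocol analysis do not use this label.

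The expected shift is about -0.016 points for three patients against a half-width of 6.93. This assumes few crossovers, at average risk. The documents report none and give no count; with none, nothing changes. A relation between crossover and IRRs could make the shift larger and could reverse its sign.

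**What to change.** For the 1st-randomized-dose Safety Population analysis and every by-dose Safety Population summary, classify each patient by the infusion actually received at that dose. Keep the ever-shorter rule only for the pooled AE tables. State which label SAP 4.5.1 means by its reference to the randomized group. Report the number of crossovers by randomized dose and direction; the deviation listing in SAP 4.2 does not require that breakdown.

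The cost is one clarifying sentence, a dose-level treatment flag and a small count table. The actual infusion is already held in the IxRS and checked against randomization (SAP 4.1, programmatic checks). Since the substudy is already unblinded, report the count first and, if any crossover occurred, add the reclassified outputs as a clearly labelled supplementary re-tabulation.
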